## **16.1 STUDY INFORMATION**

### **16.1.1 Protocol and Protocol Amendments**

- Final Study Protocol (Version 03, 13 May 2016)
- Amendment 2 (03 May 2016)
- Amendment 3 (12 May 2016)
- Amendment 4 (22 July 2016)

## HISTORY OF CHANGES

The following changes to the second version of the study protocol (22 FEB 2016) were implemented with study protocol amendment 3. These changes are non-substantial.

- Reduction of the number of PK samples in line with the adaptive feature no 13 Limit I & II.
- Correction of minor errors
- Administrative change (provider for PK analysis): Dynakin was replaced by Phinc.

The following changes to the second version of the study protocol (22 FEB 2016) were implemented with study protocol amendment 2. These changes are non-substantial. A new version of the study protocol was not issued for this amendment.

- 100% extension of Group 2 (Part A) in line with the Adaptive feature no 8, Limit I-III. This was made to gather additional pharmacokinetic information.

The following changes to the first version of the study protocol (19 JAN 2016) were implemented with study protocol amendment 1. These changes are non-substantial.

- Addition of exclusion criterion to exclude volunteers with pregnant partners due to the request of the ethics committee
- Clarification of vital signs measurements
- Clarification of holter ECG measurements

#### 4 LIST OF ABBREVIATIONS

$\gamma$ GT	: Gamma glutamyl transpeptidase
ADA	: Anti-Drug Antibody
AE	: Adverse event
Ae (0-24h)	: Cumulative amount excreted in urine from time 0 to time 24 h
ALAT	: Alanine amino transferase
ALP	: Alkaline phosphatase
API	: Active Pharmaceutical Ingredient
aPTT	: activated Partial Thromboplastin Time
ASAT	: Aspartate amino transferase
ATC	: Anatomic Therapeutic Class
AUC (0-8h)	: Area under the plasma concentration-time curve from time 0 to time 8 h
AUC (0-t)	: Area under the plasma concentration-time curve from time 0 to the time of the last quantifiable concentration
AUC (0-inf) or AUC (0-∞)	: Area under the plasma concentration time curve extrapolated to time infinity
AR	: Adverse reaction
BMI	: Body mass index
bpm	: beat per minute
CL	: Plasma clearance
C 0.25h	: Concentration at the end of the loading infusion
C 8h	: Concentration at the end of the maintenance infusion
C max	: Maximal plasma concentration
Cox-1 / 2	: Cyclo-oxygenase 1 / 2
CPK	: Creatine phosphokinase
CRF	: Case report form
C ss inf	: Steady state concentration during the maintenance infusion
CV	: Coefficient of variation
DBP	: Diastolic blood pressure
DHP	: Data Handling Protocol
EC	: Ethics Committee
ECG	: Electrocardiogram
FIH	: First in Human
h	: hour(s)
HBsAg	: Hepatitis B surface antigen
HCV	: Hepatitis C virus
HED	: Human Equivalent Dose
HIV	: Human immunodeficiency virus
HR	: Heart rate
IL	: Interleukin
IMP	: Investigational medicinal product
iNOS	: inducible Nitric Oxide Synthase
INR	: International Normalised Ratio
ITT	: Intent-to-treat
i.p.	: intraperitoneal
i.v.	: intravenous
IWRS	: Interactive Web Randomisation System
K inf	: Infusion rate
LPS	: Lipopolysaccharide
LR12	: 12 amino-acid peptidic fragment of sTLT-1
LSLV	: Last Subject Last Visit

[figure not shown]
---

$\lambda_z$	: Terminal elimination rate
MCHC	: Mean corpuscular haemoglobin concentration
MCV	: Mean corpuscular volume
MedDRA	: Medical dictionary for regulatory activities
MHC	: Mean haemoglobin concentration
MOTREM	: Investigational Medicinal Product (formulation of the active ingredient LR12)
MTD	: Maximum tolerated dose
MS	: Mass Spectrometry
NOAEL	: No-observed-adverse-effect level
PK	: Pharmacokinetics
QTcB	: QT corrected Bassett:
QTcF	: QT corrected Fridericia
SAE	: Serious adverse event
SAS®	: Statistical analysis system
SBP	: Systolic blood pressure
SD	: Standard deviation
SOC	: System organ class
SOM	: Study Operations Manual
SRC	: Safety Review Committee
SUSAR	: Suspected Unexpected Severe Adverse Reaction
$t_{1/2}$	: Terminal elimination half life
T°	: Temperature
TEAE	: Treatment-emergent adverse event
TLRs	: Toll-like Receptors
TLT-1	: TREM-Like Transcript-1
TREM-1	: Triggering receptor expressed on myeloid cells 1
$t_{max}$	: Time at which the plasma concentration maximum occurs
USP	: U.S. Pharmacopeial Convention
Vd	: Volume of distribution (CL/ $\lambda_z$ )

## 5 STUDY SYNOPSIS

Protocol No. MOT-C-104	Study Drug: MOTREM (LR12)
Title of the Study: A Phase I, randomised, placebo controlled study to assess the safety, tolerability and pharmacokinetic profiles of ascending, single, intravenous doses of MOTREM (LR12) in healthy male subjects	
Principal Investigator: [name], MD FRCA FFPM	
Study Centre: Richmond Pharmacology Ltd. St George's University of London, [name] Croydon University Hospital, Thornton Wing, [name]	
Study Period: - First enrolment expected: February 2016 - Completion date expected: June 2016	Clinical Phase: Ia (The study does not have therapeutic or prophylactic intent and does not plan to assess efficacy)
Objectives: Primary 

- To assess the safety and tolerability of MOTREM (LR12) in comparison with placebo, after single intravenous (i.v.) dose administration in healthy young male subjects

 Secondary 

- To assess the pharmacokinetics (PK) of MOTREM (LR12) after single i.v. dose administration in healthy young male subjects.

- To investigate the presence of anti-MOTREM (LR12) antibodies after single i.v. dose administration in healthy young male subjects.

	
Study Design: This study is a single center, randomised, placebo-controlled (Part B) with sequential i.v. dose escalation groups design. Single doses of MOTREM (LR12) or matching placebo (Part B) are planned to be administered following a sequential group design in 26 healthy young male subjects aged from 18 to 45 years: Part A (Groups 1 and 2 of 1 subject) followed by Part B (Groups 3 to 8 of 4 subjects each). For Part A (Groups 1 and 2), one subject each will receive MOTREM. For Part B (Groups 3 to 8) 3 subjects will receive MOTREM and 1 subject will receive placebo (3:1 ratio). Dose escalation to the following scheduled dose will only occur after satisfactory review of all safety and tolerability data by the Safety Review Committee in accordance with Table 1, protocol sections 8.2 Rules for dose escalation/progression and 8.3 Toxicity rules. Subjects will be screened within 14 days and screening may be performed over multiple days prior to entering the study on Day -1. Each subject will receive verbal and written information followed by signing of the Informed Consent Form (ICF) prior to any screening procedures taking place. Subjects will be admitted on Day 1. All the subjects from Part A (Groups 1 and 2) and Part B (groups 3 to 8) will be discharged on Day 2 after 24h post-dose (start of infusion). They will attend the unit for a follow-up visit on Day 8±1. The End of Study visit will take place on Day 28±2. All the assessments performed during the study are detailed in the Study Plan (Table 2 and Table 3). Study design features as well as number of subjects may be adapted according to Table 1.	

**Study Flowchart:**

**Number of Subjects:**

26 subjects are planned (i.e. 2 first groups of 1 healthy male subject each and 6 groups of 4 healthy male subjects). Dose groups may be amended in accordance with Table 1 to collect relevant data. The total number of subjects will not exceed 72 subjects.

**Diagnosis and Main Criteria for Admission:**

Subjects will be included if they are healthy male,  $\geq 18$  to  $\leq 45$  with a BMI between 18-30 kg/m^2 inclusive having freely given their written informed consent to participate.

Main exclusion criteria are: any clinically relevant acute or chronic diseases which could interfere with the subjects' safety during the trial, or expose them to undue risk, or which could interfere with the study objectives. Any history of drug or alcohol abuse or clinical significant disease as determined by medical history, physical examination or other evaluations.

**Part A:**

Group 1: 1 mg (loading dose) over 15 minutes i.v.;

Group 2: 10 mg (loading dose) over 15 minutes i.v.;

**Part B:**

Group 3: 0.5 mg/kg i.v. loading dose and 0.03 mg/kg/h maintenance dose i.v. over 7 hours and 45 min;

Group 4: 1 mg/kg i.v. loading dose and 0.1 mg/kg/h maintenance dose i.v. over 7 hours and 45 min;

Group 5: 2 mg/kg i.v. loading dose and 0.3 mg/kg/h maintenance dose i.v. over 7 hours and 45 min;

Group 6: 5 mg/kg i.v. loading dose and 1 mg/kg/h maintenance dose i.v. over 7 hours and 45 min;

Group 7: 5 mg/kg i.v. loading dose and 3 mg/kg/h maintenance dose i.v. over 7 hours and 45 min;

Group 8: 5 mg/kg i.v. loading dose and 9 mg/kg/h maintenance dose i.v. over 7 hours and 45 min.

Please refer to Table 1.

**Reference Treatment(s) and Mode of Administration:**

Placebo solution: saline; i.v. administration

**Anticipated Duration of Treatment:**

Single dose administration.

Part A (Groups 1 and 2): 15 minutes i.v. dose

Part B (Groups 3 to 8): 7 hours and 45 minutes continuous i.v. administration after a 15 minutes i.v. loading dose.

**Criteria for Evaluation:**

Please refer to the Study Plan (Table 2 and Table 3) for detailed timing of the evaluations.

**Safety Parameters:**

- Vital signs: systolic (SBP) and diastolic (DBP) blood pressure, heart rate, and body temperature (tympanic).
- ECG (12-lead ECG, telemetry and Holter)
- Physical examination.

---

- Safety laboratory tests: haematology, coagulation, plasma biochemistry, urinalysis.
- Local tolerability at the infusion site.
- Presence of anti-LR12 antibodies
- Adverse events: from screening until study completion.

#### **Pharmacokinetics:**

Plasma concentrations of LR12 will be measured by a validated LC-MS/MS assay and analysed using non-compartmental methods to obtain estimates of the following PK parameters:  
 $C_{\max}$ ,  $t_{\max}$ ,  $C_{0.25h}$ ,  $C_{8h}$ ,  $C_{ss\ inf}$ ,  $AUC_{0-0.25h}$ ,  $AUC_{0-8h}$ ,  $AUC_{0-t}$ ,  $AUC_{0-\infty}$ ,  $t_{1/2}$ ,  $\lambda_z$ ,  $CL$ ,  $V_d$ .

---

#### **Statistical Methods:**

##### **Adverse Events:**

Adverse events will be coded using the MedDRA dictionary version 17.1 or higher. They will be classified by System Organ Class and Preferred Term.

The number and percentage of subjects with at least one adverse event will be provided.

##### **Analysis of treatment-emergent adverse events (TEAE)**

TEAEs will be summarised and described for the following criteria:

- Number and percentages of subjects with at least one TEAE
- Number and percentages of subjects with at least one severe TEAE
- Number and percentages of subjects with at least one study treatment related TEAE
- Number and percentages of subjects with at least one serious TEAE
- Number and percentages of subjects with at least one TEAE leading to treatment withdrawal

The maximum intensity encountered during the evaluation period will be recorded.

The number of TEAEs of each category will also be provided by system organ class and preferred term.

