#### **6.4.2 Potential Risks**

##### **6.4.2.1 Nonclinical Safety Pharmacology and Toxicology:**

Toxicity studies were only conducted in one species in accordance with ICH guidance documents S6(R1) and M3(R2) as well as to EMA’s guidance on repeated dose toxicity (EMEA/CHMP/SWP/488313/2007). Safety pharmacology also followed the ICH S7A and S7B guidance.

A cardiovascular safety study in Cynomolgus monkeys did not identify any adverse cardio-vascular effect of LR12, when administered as an intravenous infusion of 18-times the expected pharmacologically active dose. In addition, the central nervous and pulmonary systems were explored during the toxicity studies and did not unveil untoward effects.

Receptor binding assays with a wide range of receptors did not show any relevant off target effects in vitro.

A bacterial reverse mutation test (Ames test) and a chromosome aberration test did not show any evidence for genotoxicity of LR12.

Toxicokinetic studies showed dose-dependent kinetics and suggested a clearance of the product within 15 to 30 minutes depending on the dose.

A series of toxicity studies was conducted with LR12 in cynomolgus monkey, as this represents the only relevant species. In the pivotal 14-day toxicology study with the clinical formulation, the administration of LR12 was safe and well tolerated at doses 7.2, 24 and 140 mg/kg/day. No adverse events were observed up to the highest dose level. In addition, a dose of 440 mg/kg/day in a preliminary formulation was found to be safe and well tolerated in a 14-day study.

Severe time dependent adverse events, likely related to immunogenicity, were observed in the low- dose arm of an early toxicity study conducted with an experimental frozen formulation that was diluted with a technical, non USP grade buffer. Further toxicology studies with a suitable buffer or the API alone and with the final clinical formulation did not reproduce these findings.

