#### **6.4.2.2 Clinical Studies**

There is currently no clinical experience with MOTREM. Potential risks will be closely monitored for as part of the safety evaluations being performed in this study.

Measures to minimise the risks to volunteers will include:

- Selection of a starting dose well below a dose level for which effects are expected  
Please refer to protocol section [8.4.1](#).
- Sentinel dosing of subjects. Please refer to protocol section [8.4.4](#).
- Progression to next dose level only after evaluation of data from previous groups/cohorts and approval from Safety Review Committee (SRC). Please refer to protocol section [8.2.3](#) and [8.2.4](#).
- Clinical and laboratory monitoring of study subjects. Please refer to protocol section [8.2.2](#) and [12.1.2](#).
- Exposure to study drug limited to 8 hours. Please refer to protocol section [8.4.1](#).

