**Spontaneously reported SAEs will be collected until 30 days following the final study visit.**

**SAEs experienced after this 30-day period will only be reported if the investigator suspects a causal relationship with the study drug.**

Adverse events (AEs) will be recorded in the CRF throughout the study from day of consent (screening visit) until the last follow up assessment.

Any AEs that are unresolved at the subject's last AE assessment in the study (i.e. at the end of study visit) are to be followed up by the Investigator for as long as medically indicated. INOTREM SA retains the right to request additional information for any subject with ongoing AE(s)/SAE(s) at the end of the study, if judged necessary.

Findings and values related to physical examinations and measurements of ECG, vital signs, (tympanic temperature, blood pressure, and heart rate) and laboratory parameters will be defined as AEs if they are considered clinically relevant deteriorations compared with screening values, as judged by the PI.

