#### **Analysis of treatment-emergent adverse events (TEAE)**

Only TEAE will be summarised and described for the following criteria:

- Number and percentages of subjects with at least one TEAE
- Number and percentages of subjects with at least one severe TEAE
- Number and percentages of subjects with at least one study treatment related TEAE
- Number and percentages of subjects with at least one serious TEAE
- Number and percentages of subjects with at least one TEAE leading to treatment withdrawal

The maximum intensity encountered during the evaluation period will be checked.

The number of TEAE of each category will also be provided by system organ class and preferred term.

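### No TEAE summary is split by time of onset, so if the TEAE period runs to the last visit, later background events shrink the LR12–placebo difference caused by an infusion of at most 8 hours

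*Combined protocol and SAP*

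**What the plan says.** Section 15.1.3 states "Only TEAE will be summarised and described for the following criteria", and then lists five criteria. The first is "Number and percentages of subjects with at least one TEAE"; the others cover severe, treatment-related, serious, and withdrawal-leading TEAEs, with counts by system organ class and preferred term. The synopsis has the same list. Neither divides events by onset, and both refer to maximum intensity over an evaluation period that is not defined.

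The list of abbreviations expands TEAE as "Treatment-emergent adverse event" and goes no further. No section gives the start or end of the treatment-emergent period.

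Collection of AEs is defined. The synopsis has "Adverse events: from screening until study completion", and section 13.1.2 has "Adverse events (AEs) will be recorded in the CRF throughout the study from day of consent (screening visit) until the last follow up assessment". On the last visit, the synopsis says "The End of Study visit will take place on Day 28±2".

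Exposure is short. Section 6.4.2.2 lists "Exposure to study drug limited to 8 hours" among the risk-reduction measures. Section 6.4.2.1 reports that the toxicokinetic studies "suggested a clearance of the product within 15 to 30 minutes depending on the dose". Section 8.4.1 expects human clearance to be similar to that in monkeys.

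The named risks differ in timing. Infusion and hypersensitivity reactions (6.4.2.3) are watched for during and after administration. A possible antibody response (6.4.2.4) is the stated reason for following subjects for 28 days.

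**The concern.** The primary objective is safety and tolerability compared with placebo. If every post-dose event up to the last visit is a TEAE, a subject with a cold on Day 20 and a subject who reacts during the infusion count alike in the any-TEAE line. A subject who has any later background event is in the numerator anyway, so an infusion effect in that subject no longer changes the percentage. The headline contrast then understates an acute effect, and early and delayed risks are mixed. Part B randomises only 18 subjects to LR12 and 6 to placebo, so there is little precision to lose.

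**Working it through.** **Inputs from the protocol.** Part B has six groups of four at 3:1, so 6 × 3 = 18 on LR12 and 6 × 1 = 6 on placebo. With Part A, 2 × 1 + 6 × 4 = 26, which reproduces the planned total. Section 15.4 reports no formal power calculation, so there is no power figure to reproduce.

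**Lengths of the periods.** Day 1 to Day 28 is 27 days, or 27 × 24 = 648 h. That is 648 / 8 = 81 times the longest exposure (75 to 87 times for Day 26 to Day 30). The infusion is 8 / 648 = 1.2% of the period.

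**Assumptions (no AE rate is in the documents).** Let b1 be the background risk of at least one event in the early period, b2 the background risk in the later period, and q the probability that the infusion causes an early event in an LR12 subject who would otherwise have none. Treat these as independent.

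- Early period: placebo b1; LR12 1 − (1 − b1)(1 − q); difference (1 − b1)q.
- Whole period: placebo 1 − (1 − b1)(1 − b2); LR12 1 − (1 − b1)(1 − b2)(1 − q); difference (1 − b1)(1 − b2)q.
- Ratio of whole to early: 1 − b2, whatever b1 and q are.

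**Results for q = 0.5 and b1 = 0.10**, taking the first 24 h as the early period. The SE is from independent binomials with 18 and 6 subjects. Power is for the two-sided Fisher test at 5%, by full enumeration.

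| Period | LR12 | Placebo | Difference | Difference/SE | Power |
|---|---|---|---|---|---|
| First 24 h | 55% | 10% | 45 points | 2.65 | 0.32 |
| Whole, b2 = 0.10 | 59.5% | 19% | 40.5 points | 2.05 | 0.25 |
| Whole, b2 = 0.30 | 68.5% | 37% | 31.5 points | 1.40 | 0.17 |
| Whole, b2 = 0.60 | 82% | 64% | 18 points | 0.83 | 0.12 |

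For example, at b2 = 0.30 the difference is 0.9 × 0.7 × 0.5 = 0.315.

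**Smaller effect, q = 0.3, b1 = 0.10.** The early difference is 0.9 × 0.3 = 27 points (difference/SE 1.62). Over the whole period it is 18.9 points at b2 = 0.30 (0.82) and 10.8 points at b2 = 0.60 (0.49). Power is about 5% in each case, so the split does nothing useful for a test.

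**Background concentrated on the dosing day.** With q = 0.5, b1 = 0.30 and b2 = 0.10, the difference is 35 points early against 31.5 overall, and power is 0.18 against 0.17. The split then gains little.

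**The case against.** **The TEAE period is not stated.** A reader might infer that the plan fixes it as dosing to Day 28. The documents do not support that: they define when AEs are collected, not which count as treatment-emergent. Section 15.1 also refers to a statistical analysis plan to be agreed with the sponsor. This stands, and it makes the dilution conditional. No text given here ends the period earlier.

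**The plan does not rest on one number.** There are five criteria, plus counts by system organ class and preferred term. A cold and an infusion reaction separate by preferred term, and the related-TEAE line removes some background. This stands in part. The related line depends on investigator judgement, and section 13 counts an event as related whenever a relationship cannot be excluded. The term counts carry no timing.

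**Acute tolerability is examined elsewhere.** Vital signs, ECG and infusion-site checks are timed around the infusion, vital signs and ECG are described by time point, and escalation needs at least 24 h of safety data. A reader might infer that an infusion effect would go unseen; these measures show otherwise. None of them, however, gives a between-arm AE summary by period.

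**The size is assumed.** This stands. The model also gives all 18 LR12 subjects the same effect although their doses differ widely. An effect confined to the higher doses would be weaker in either period.

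**The analysis is mostly descriptive.** Section 15.4 says so. Power is therefore a secondary argument, but dilution alters the descriptive estimate itself.

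**Conclusion.** The point holds as a low-cost improvement to the placebo comparison. No TEAE criterion is split by onset, and nothing ends the treatment-emergent period before Day 28±2. If TEAEs run to that visit, the infusion-caused any-TEAE difference is reduced by the factor (1 − later background rate): a relative loss of 10%, 30% or 60% at later background of 10%, 30% or 60%. The factor is exact under independence, but the rates are illustrative because the documents supply none. The benefit lies mainly in a clearer descriptive estimate and in separating early from delayed events.

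The calculation might tempt a reader to make the first 24 hours the main comparison. The documents do not support such a hierarchy: the trial has no formal power calculation, and section 6.4.2.4 gives a stated reason for watching later events. The clearance time is also a preclinical figure, only expected to carry over to humans, so it cannot by itself set the end of the TEAE period.

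**What to change.** In the synopsis and section 15.1.3, report each TEAE criterion by IMP in three columns:

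1. onset on Days 1–2 (the in-house stay);
2. onset after Day 2 to End of Study;
3. overall.

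State the start and end of the treatment-emergent period in the same place, so that the columns have fixed limits. Note under the table that a subject may count in both periods, so the first two columns need not add up to the third. Do not rank the periods.

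The Days 1–2 split needs only the onset date, which section 13.1.2 already lists. An exact 24-hour cut falls within Day 2, and that section does not list onset time. If that cut is preferred, add AE onset time to the CRF for Days 1–2.

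The cost is two extra columns per table and one more descriptive split with small counts in each period, particularly among the 6 placebo subjects. No event is dropped.

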#### **Analysis of Deaths and Other Serious Adverse Events**

A listing of deaths will be provided.

A summary table of the other serious adverse events should be provided. In case of a low incidence of serious adverse events, only a listing will be done.

